13 STATISTICAL CONSIDERATIONS

13.1 DETERMINATION OF SAMPLE SIZE

Phase I part:

The Phase I part of this study aims to determine the safety and tolerability of isatuximab. It is anticipated that up to 6 to 12 evaluable patients will be enrolled. Patient(s) not evaluable for DLT will be replaced.

Phase II part:

The Phase II part of the study aims to evaluate 33-36 subjects which include the subjects in Phase I part at the recommended dose level. Given an assumed true ORR of 28%, the null hypothesis ORR $\leq 10\%$ will be rejected using an exact binomial test at a one-sided alpha of 0.025 with at least 80% power, if the observed ORR is greater than or equal to 24.2% (ie, 8 responders). The sample size calculation was performed using SAS ver. 9.4 SAS/STAT 13.2, power procedure.

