	
Phase II Part
 
The phase II part of the study aims to evaluate 33-36 patients which include the subjects in Phase I part at the recommended dose level. Given an assumed true ORR of 28%, the null hypothesis ORR \leq10% will be rejected using an exact binomial test at a one-sided alpha of 0.025 with at least 80% power.
 
Analysis populations
 
For both Phase I and Phase II parts of the study, the all treated/safety population will include all patients who have given their informed consent and who have received at least one dose (even incomplete) of Isatuximab. This population is the primary population for the analyses of efficacy and safety parameters. All analyses using this population will be based on the dose level actually received. In the Phase I part, the DLT evaluable population is the subset of patients from the all treated population who have completed the first cycle which consists of 4 administrations of the IMP, or they discontinued the IMP before completion of Cycle 1 for a DLT. The dose escalation will be determined on the DLT evaluable population.
 
The pharmacokinetic population is the subset of patients from the all treated population who have a PK parameter.
 
The activity/efficacy population is the subset of patients from the all treated population who have evaluable data for exploratory analysis.
 
General statistical approach
 
Basically, data from initial dose level and recommended dose level will be analyzed and reported separately. Only the efficacy evaluated in Phase I Cohort 2 and Phase II part is combined for recommended dose level. The separate tables will be presented by phase (when appropriate) unless otherwise noted.
 
Analysis of safety endpoints:
 
IMP related DLTs will be assessed and analyzed on DLT evaluable population.
 
The same analysis below using all treated/safety population will be applied in Phase I and Phase II part.
 
The treatment emergent adverse events (TEAEs) will be coded according to Medical Dictionary for Regulatory Affairs (MedDRA). Adverse events and laboratory abnormalities will be graded according to the NCI-CTCAE v. 4.03. Number (%) of patients experiencing treatment-emergent adverse events by primary system organ class and preferred term will be summarized by CTCAE grade (all grades and Grade \geq3) for the safety population. The same table will be prepared for drug related TEAEs, TEAEs leading to treatment discontinuation, serious TEAEs, TEAEs with fatal outcome, and drug-related SAEs occurred during the post treatment dosing period.
 
Number (%) of patients with laboratory abnormalities (ie, all grades and Grade \geq3) using the worst grade during the on-treatment period will be provided for the safety population.
 
The descriptive statistics of all vital signs' variable will be calculated.
 
Analysis of pharmacokinetic and immune response endpoints:
 
The same analysis will be applied in Phase I and Phase II part.
 
Pharmacokinetic and immune response endpoints and CD38 receptor density will be assessed and analyzed on PK population or activity/efficacy population.

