13.3.2 Patients Evaluable for DLT Assessment

The DLT evaluable population is only applicable to the Phase I part of the study.

The DLT evaluable population is the subset of patients from the all treated population who have completed the first cycle which consists of 4 administrations of the IMP, or they discontinued the IMP before completion of the first cycle for a DLT. In practice, a “Dose-Limiting Toxicities” form should have been filled in at the end of Cycle 1. If there are missing or incomplete data that influence the evaluation of DLT, the patient will not be evaluable for DLT. Patients excluded from this population will be replaced.

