13.4.8.1 Efficacy endpoints for Phase I part of the study

Best overall response, OS, PFS, TTP, and DOR will be listed along with relevant patient/disease characteristics.

13.4.8.2 Analysis of primary efficacy endpoint for Phase I (Recommended dose level) and Phase II part of the study

Analysis of efficacy endpoint will be performed on all patients who received at least one dose of recommended dose across Phase I and II part:

ORR and the 95% two-sided confidence interval will be computed using Clopper-Pearson method. The null hypothesis that the true response rate (ORR) is <10% will be tested using a one-sided exact binomial test with a significance level of 0.025.

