### **1.3 DETERMINATION OF SAMPLE SIZE**

The phase 2 part of the study aims to evaluate 33-36 subjects which include the subjects in Phase 1 part at the dose level determined as MTD/recommended dose. Given an assumed true ORR of 28%, the null hypothesis ORR  $\leq 10\%$  will be rejected using an exact binomial test at a one-sided alpha of 0.025 with at least 80% power, if the observed ORR is greater than or equal to 24.2% (i.e., 8 responders). The sample size calculation was performed using SAS ver. 9.4 SAS/STAT 13.2, power procedure.

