##### ***2.4.4.1 Analysis of primary efficacy endpoint***

The primary analysis is based on the dose level determined as MTD combined in phase 1 and phase 2. ORR as assessed by IAC will be summarized. The null hypothesis that the true response rate (ORR) is <10% will be tested using a one-sided exact binomial test with a significance level of 0.025. A 95% two-sided confidence interval will be computed for ORR using Clopper-Pearson method.

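### The stated power of at least 80% does not hold at 33 or 34 patients: exact power there is 74.5% and 77.6%

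*Protocol*

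**What the plan says.** Protocol section 13.1 sets the size of the primary analysis: "The Phase II part of the study aims to evaluate 33-36 subjects which include the subjects in Phase I part at the recommended dose level". It continues "Given an assumed true ORR of 28"%, with a null ORR of 10% or less, an exact binomial test at one-sided 0.025, and rejection "with at least 80% power, if the observed ORR is greater than or equal to 24.2% (ie, 8 responders"). The calculation is attributed to the SAS power procedure.

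Phase 2 SAP section 1.3 carries the same claim and threshold: "with at least 80% power, if the observed ORR is greater than or equal to 24.2% (i.e., 8 responders"). The Phase II sample-size paragraph of the protocol synopsis makes the power claim without a threshold: the null "will be rejected using an exact binomial test at a one-sided alpha of 0.025 with at least 80% power". None of the three places limits the 80% to part of the 33 to 36 range.

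The analysis itself is specified separately. In SAP section 2.4.4.1 the null hypothesis "will be tested using a one-sided exact binomial test with a significance level of 0.025", with a Clopper-Pearson interval. Protocol section 13.4.8.2 and the synopsis specify the same test. None of these analysis sections uses 24.2%.

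**The concern.** A power stated as a minimum for a range of sample sizes has to hold at the worst point of the range. With an exact test, power depends on the integer critical count. If that count stays the same from 33 to 36 patients, power must rise with the number of patients and be lowest at 33. The only percentage in the sentence, 24.2%, is 8/33 and so belongs to that smallest size.

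This is the study's only formal hypothesis test. If the smallest planned size does not reach 80%, the sample-size text overstates the chance of detecting the assumed effect. A narrow failure would then be judged against a power the design did not have.

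**Working it through.** **Inputs.** Null ORR 0.10, assumed ORR 0.28, one-sided 0.025, exact binomial test, N = 33 to 36 (protocol 13.1; SAP 1.3). The analysis set is "all patients who received at least one dose of recommended dose across Phase I and II part" (protocol 13.4.8.2), so every treated patient counts and there is no attrition margin to explain the lower end.

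**Formulas.** Critical count c = the smallest integer with P(X ≥ c | N, 0.10) ≤ 0.025. Power = P(X ≥ c | N, 0.28) = Σ from k = c to N of C(N,k) · 0.28^k · 0.72^(N−k).

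**What reproduces.** At N = 33, P(X ≥ 7 | 0.10) = 0.0417, which exceeds 0.025, and P(X ≥ 8 | 0.10) = 0.0141, which does not. So c = 8, and 8/33 = 24.24%. The plan's count and percentage are both right for N = 33.

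**What does not reproduce.** The power, taken across the range:

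| N | P(X≥7), ORR 0.10 | P(X≥8), ORR 0.10 | c | 8/N | Power at ORR 0.28 | Against 80% |
|---|---|---|---|---|---|---|
| 33 | 0.0417 | 0.0141 | 8 | 24.2% | 74.5% | −5.5 points |
| 34 | 0.0481 | 0.0169 | 8 | 23.5% | 77.6% | −2.4 points |
| 35 | 0.0552 | 0.0200 | 8 | 22.9% | 80.5% | met |
| 36 | 0.0628 | 0.0235 | 8 | 22.2% | 83.0% | met |

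Type II error is 100 − 74.5 = 25.5% at N = 33 and 100 − 77.6 = 22.4% at N = 34. For 80% power with c = 8, the true ORR would have to be about 29.5% at N = 33 and 28.6% at N = 34.

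**Other methods that might have produced 80%, at N = 33 and 34.**
- Mid-p: 74.5% and 77.6%.
- Continuity-corrected normal approximation: 78.8% and 79.9%.
- Uncorrected normal approximation: 84.0% and 84.8%, but this is not the stated exact test.
- Exact test at one-sided 0.05: 85.7% and 87.8%, but with c = 7, which contradicts both the stated alpha and the 8 responders.

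Nothing that keeps the exact test, one-sided 0.025 and 8 responders reaches 80% at either size.

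**The percentage read literally.** 0.242 × 33 = 7.99, so 8 responders. 0.242 × 34 = 8.23, 0.242 × 35 = 8.47 and 0.242 × 36 = 8.71, so 9 responders each time. Requiring 9 would give power of 64.2%, 68.0% and 71.5%. The percentage and the count agree only at N = 33.

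**Which N is plausible.** The synopsis expects approximately 30 Phase II patients. A 3-patient recommended-dose cohort with no DLT (protocol 6.2.2) gives 30 + 3 = 33. N can be higher, because a treated Phase I patient who is not DLT-evaluable is replaced (protocol 13.3.2: "Patients excluded from this population will be replaced") but still belongs to the primary analysis set. A small overshoot does not rescue the claim. At N = 37, 8 responders give p = 0.0274, so c becomes 9 and power is 74.7%. At N = 38 power is 77.7%, and it passes 80% again at N = 39 (80.4%).

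**The case against.** The arithmetic is hard to dispute, so the case on the other side is about weight.

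- **Timing.** The rationale for Amendment 04 (Appendix J, December 2018) already refers to results seen at the first analysis, and section 6.7.2 makes the first cutoff the ORR analysis. The protocol reviewed is Amendment 05 of July 2020. Prospective power could no longer influence enrolment, and section 17 generally requires IRB review of an amendment, so a clarification in the study report might serve as well. This limits the practical effect of a correction but does not make the sentence true.
- **Inference is untouched.** The decision rule is the exact test at 0.025, and 24.2% plays no part in it. This stands in full.
- **Half the range is correct.** The claim holds at 35 and 36. The 2.4-point gap at 34 would close with a true ORR of about 28.6%, a small change beside the uncertainty in 28% itself, a figure that matches an ORR seen in 25 patients (protocol 4.3.1). This is fair for N = 34. The 5.5 points at N = 33 are not trivial, and 33 is a realistic size.
- **24.2% may only illustrate the smallest N.** That reading is possible. The text does not say so, and on that reading the sentence points to the size where the power claim fails most clearly.
- **N = 37 and 38 lie outside the plan.** Agreed. The dip there is ordinary binomial discreteness and adds no weight to the finding.

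**Conclusion.** The concern holds. Under the plan's own inputs (null ORR 10%, true ORR 28%, exact test, one-sided 0.025), power is 74.5% at 33 patients and 77.6% at 34, so the minimum of 80% is overstated by 5.5 and 2.4 points. It is met at 35 and 36. The threshold of 24.2% equals 8 responders only at N = 33.

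This is an error in a stated design property, made in protocol 13.1, SAP 1.3 and, for power alone, the synopsis. It does not affect the test, its type I error, the estimate or the interval. It should be corrected, but it does not threaten the analysis. The result rests on no assumption beyond the documents' figures. How far it matters in practice depends on the number of patients treated at the recommended dose.

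**What to change.** In protocol 13.1, the synopsis and SAP 1.3, replace the 80% claim with exact power by size: 74.5% (N = 33), 77.6% (34), 80.5% (35) and 83.0% (36), with actual one-sided alpha of 0.0141, 0.0169, 0.0200 and 0.0235.

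In protocol 13.1 and SAP 1.3, define success as an exact one-sided p-value of at most 0.025, matching the test already specified in the analysis sections. Give 8 responders at N = 33 to 36 as an illustration only, noting that 9 are needed at N = 37. Delete 24.2% or write it as 8/33 at N = 33.

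The change is to wording only, with no extra patients and no change to the test or analysis. The costs are a less favourable stated power and whatever review a protocol amendment requires. If the documents are not amended again, the same correction belongs in the study report.

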13.2 PATIENT DESCRIPTION

13.2.1 Disposition of Patients

The number of screened patients as well as the number and percentage of patients included in the analysis populations defined in [Section 13.3](#) will be provided. Reasons for treatment discontinuation will be summarized using the all treated/safety population.

13.2.2 Protocol Deviations

All critical or major deviations potentially impacting evaluation of the MTD (Phase I part only), efficacy analyses, as well as drug-dispensing irregularities and other major or critical deviations will be summarized in tables giving numbers and percentages of patients with deviations, or only the listing will be provided.

13.3 ANALYSIS POPULATIONS

13.3.1 All-treated/safety Population

For both Phase I and Phase II parts of the study, the all treated/safety population will include all patients who have given their informed consent and who have received at least one dose (even incomplete) of isatuximab.

This population is the primary population for the analyses of efficacy and safety parameters. All analyses using this population will be based on the treatment actually received.

13.3.2 Patients Evaluable for DLT Assessment

The DLT evaluable population is only applicable to the Phase I part of the study.

The DLT evaluable population is the subset of patients from the all treated population who have completed the first cycle which consists of 4 administrations of the IMP, or they discontinued the IMP before completion of the first cycle for a DLT. In practice, a “Dose-Limiting Toxicities” form should have been filled in at the end of Cycle 1. If there are missing or incomplete data that influence the evaluation of DLT, the patient will not be evaluable for DLT. Patients excluded from this population will be replaced.

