6.5 DOSE DELAYS/ MODIFICATIONS

In this study, Cycle 1 consists of 4 isatuximab administrations and consecutive cycles consist of 2 isatuximab administrations.

A dose delay of up to 2 weeks is permitted in order for a patient to recover to their baseline status (see [Section 6.4](#)) or to accommodate scheduling issues (eg, holidays, weather, etc.). In case of a delay greater than 2 weeks the patient will be withdrawn from the treatment as per the investigator and the Sponsor decision. Exceptions allowed by the investigator and the Sponsor should be considered only for patients with clear objective clinical benefit.

Intra-patient dose and schedule modifications are not allowed.

6.6 GUIDELINES FOR MANAGEMENT OF ADVERSE EVENTS:

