6.6.2 Management of Potential Tumor Lysis Syndrome

General guidelines for the management of the tumor lysis syndrome are provided in [Table 4](#).

Table 4 - Tumor lysis syndrome management

Symptom	Recommended Action
Laboratory Tumor Lysis Syndrome (LTLS): 
• ≥ 2 simultaneous abnormalities within 3 days prior to and up to 7 days after start of treatment• Uric acid >8 mg/dL (>475.8 μmol/L)• Potassium >6.0 mmol/L• Phosphorus >4.5 mg/dL (>1.45 mmol/L) Corrected calcium <7.0 mg/dL (<1.75 mmol/L) or ionized calcium <1.12 mg/dL (<0.3 mmol/L) ^a	Omit isatuximab until all serum chemistries have resolved Ensure normal hydration; correct laboratory abnormalities, fluid overload, electrolyte or acid-based deviations Monitor TLS complications including renal functions Refer to "serious adverse drug reaction countermeasure manual" for TLS treatment ^b . Reinstitute isatuximab treatment at full doses after resolution
Clinical TLS (CTLS): meeting criteria for LTLS in addition to one of the following complications, 
• Acute kidney injury: increase in the serum creatinine level of 0.3 mg/dL (26.5 μmol/L) or the presence of oliguria, defined as an average urine output of <0.5 mL/kg/hr for 6 hrs.• Seizures, cardiac dysrhythmia, neuromuscular irritability (tetany, paresthesias, muscle twitching, carpopedal spasm, Trousseau's sign, Chvostek's sign, laryngospasm, bronchospasm), hypotension, or heart failure probably or definitely caused by hypocalcemia• Dysrhythmia probably or definitely caused by hyperkaliemia	

a The corrected calcium level in milligrams per deciliter = measured calcium level in milligrams per deciliter + $0.8 \times (4 \text{-albumin in grams per deciliter})$

b Serious adverse drug reaction countermeasure manual for TLS: <http://www.mhlw.go.jp/topics/2006/11/dl/tp1122-1e17.pdf>
MHLW site: http://www.mhlw.go.jp/stf/seisakunitsuite/bunya/kenkou_iryou/iyakuhin/topics/tp061122-1.html

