11.2 REPLACEMENT OF PATIENTS

During the Phase I part of the study, a patient may be considered not evaluable for DLT and may be replaced at the same dose level as described in [Section 6.3](#).

Patients treated in the Phase II part of the study who are withdrawn from study treatment will not be replaced.

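### The DLT-evaluable definition leaves out, and replaces, a patient who has a Cycle 1 DLT but neither receives four administrations nor stops because of the DLT

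*Protocol*

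**What the plan says.** **The definition.** Protocol 13.3.2 gives two routes into the DLT-evaluable population. The first takes in treated patients "who have completed the first cycle which consists of 4 administrations of the IMP". The second, and only alternative, is worded: "or they discontinued the IMP before completion of the first cycle for a DLT". A further sentence deals with missing data: "If there are missing or incomplete data that influence the evaluation of DLT, the patient will not be evaluable for DLT". The consequence for those left out is then given: "Patients excluded from this population will be replaced". Phase 1 SAP 2.3.2 repeats all of this. The synopsis (Analysis populations) gives the same two routes and states: "The dose escalation will be determined on the DLT evaluable population". Protocol 13.1, the synopsis sample-size text and Phase 1 SAP 1.3 also say that non-evaluable patients are replaced.

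**Text that differs.**
- Protocol 11.2 makes replacement optional: "a patient may be considered not evaluable for DLT and may be replaced at the same dose level". It refers to 6.3 for the details, but 6.3 contains no replacement rule.
- Protocol 6.3 sets the maximum administered dose (MAD) by DLTs in at least 2 of at most 6 treated patients. The synopsis (Study design) uses evaluable patients for the same threshold.
- Protocol 13.4.4.1 summarises DLTs on the evaluable population. The adverse event overviews in Protocol 13.4.4.2 and Phase 1 SAP 2.4.5.1 include DLTs on all treated patients.

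**The decision rule.** Under Protocol 6.2.2 (Table 2), 0/3 means proceed, 1/3 means expand to six, 1/6 means proceed, and two or more DLTs define the MAD. Protocol 6.2, 6.9.1 and 9.1.1 give the Study Committee the safety data and the potential DLTs before each step.

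**The concern.** A DLT-evaluable set should keep every patient who had a DLT and exclude only DLT-free patients who were not observed long enough to be informative. Here a patient with a DLT is kept only if one of two further conditions is met: all four administrations were given, or treatment was stopped because of the DLT. The reason for stopping is a recorded field, and Protocol 11.1.1 lists others, including progression and withdrawal of consent.

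Escalation and the move to Phase II rest on 3 to 6 patients per cohort, so one DLT can decide the outcome. The excluded patient is replaced. The lost DLT can therefore leave the decision unchanged or make it less strict, but never stricter.

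**Working it through.** **1. The plan's threshold.** 2/6 = 33.3%, which agrees with the 33% stated in 6.3. The neighbouring proceed outcome is 1/6 = 16.7%.

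**2. Who is evaluable.** Patients with a Cycle 1 DLT under the two routes in 13.3.2:

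| Course after the DLT | Four administrations? | Stopped for a DLT? | Evaluable? |
|---|---|---|---|
| Delayed, then all four given | yes | no | yes |
| Stopped because of the DLT | no | yes | yes |
| Dose held, then stopped for progression or withdrawal of consent | no | no | **no, replaced** |
| A dose missed and not made up, treatment continues | no | no | **no, replaced** |

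The third row can occur because 6.4 requires recovery before the next dose, so a DLT during weekly dosing can lead to a hold in which something else ends treatment. The fourth is possible because the plan does not say whether a missed Cycle 1 dose must be made up. The missing-data sentence in 13.3.2 makes no express exception for a confirmed DLT either.

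**3. Effect on the count.**
- *First three patients.* A has a counted DLT, B has a DLT but falls in the gap, C has none. Counting treated patients gives 2/3, so the MAD is reached. Under 13.3.2, B is replaced. If the replacement is DLT-free the count is 1/3 and the cohort expands. If the next three are DLT-free it is 1/6, so proceed, although 2 of 7 treated patients (28.6%) had a DLT.
- *Second three patients.* After 1/3, a DLT in the gap would have made 2/6 (stop). With a DLT-free replacement it becomes 1/6 (proceed).
- *Only DLT.* If B's is the only DLT among the first three and the replacement is DLT-free, 1/3 (expand) becomes 0/3 (proceed without expansion).

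**4. Illustrative probabilities.** Let p be the true DLT rate and s the share of DLT patients who fall in the gap and are replaced. Neither is in the documents; both are assumed.

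- P(proceed) = (1−p)³ + 3p(1−p)² × (1−p)³
- Counted DLT rate with replacement: p′ = p(1−s)/(1−ps), used in place of p

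At p = 1/3 and s = 0: (2/3)³ = 0.296; 3 × (1/3) × (2/3)² = 0.444; P = 0.296 + 0.444 × 0.296 = 0.428.

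| s (assumed), p = 1/3 | p′ | P(proceed) |
|---|---|---|
| 0 | 0.333 | 0.428 |
| 0.1 | 0.310 | 0.473 |
| 0.2 | 0.286 | 0.524 |
| 0.3 | 0.259 | 0.580 |

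Other assumed true rates show the same direction:

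| p (assumed) | s = 0 | s = 0.10 | s = 0.25 |
|---|---|---|---|
| 0.20 | 0.709 | 0.744 | 0.798 |
| 0.30 | 0.494 | 0.539 | 0.614 |
| 0.40 | 0.309 | 0.351 | 0.428 |

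All these figures suppose that the committee follows the formal count and does not act on the dropped event.

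**The case against.** **The committee would know.** A reader might infer that the DLT disappears from the escalation decision. The documents do not support that. Section 6.2 bases the decision on Cycle 1 DLTs validated by the Study Committee and adds cumulative toxicities. Section 6.9.1 sends the committee the adverse event and DLT forms before each decision, and 9.1.1 requires review of all safety data and potential DLTs. DLTs are also reported as events of special interest within 24 hours (10.5.5). This mitigation stands: the event leaves the formal count, not the committee's sight. It does not correct the definition. The stated purpose of the 9.1.1 review is to judge relationship to the drug, and 6.9.1 has the committee confirm escalation in line with the protocol, whose synopsis names the evaluable population.

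**Most DLTs are covered.** This also stands. Delay of up to 14 days is allowed in Cycle 1 (9.1.1), and a patient who still receives four administrations is evaluable. Delay beyond 14 days from toxicity is itself a DLT and normally ends treatment under 6.5, which fits the second route. It would be wrong to infer that a DLT managed without stopping treatment generally falls in the gap.

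**Two texts that seem to widen the gap do not.**
- The tumour lysis guidance in Table 4, "Omit isatuximab until all serum chemistries have resolved", might suggest skipped Cycle 1 doses. The same table then has treatment reinstituted after resolution, so it reads as a hold. In addition, 9.1.1 excludes Grade 3 to 4 electrolyte abnormalities from the DLTs.
- The allowance in 6.5, "Exceptions allowed by the investigator and the Sponsor should be considered only for patients with clear objective clinical benefit", lets a patient continue after a long delay. A patient who then completes four administrations is evaluable, so it creates no exclusion by itself.

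**The size is unknown.** Correct. The share of DLT patients affected has no basis in the documents.

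**It is too late to change escalation.** Also correct. The Amendment 04 rationale (Appendix J, December 2018) refers to results already seen at the Phase II first analysis, and the current protocol dates from July 2020. What remains is the reported DLT count and the definition itself.

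**Conclusion.** The point holds as a narrow defect in a population definition. Applied literally, 13.3.2, the synopsis and Phase 1 SAP 2.3.2 drop a patient with a real Cycle 1 DLT who has fewer than four administrations and did not stop for the DLT. That patient leaves the formal 3+3 count and the DLT summary in 13.4.4.1, yet stays in the all-treated overviews, so two tables could give different DLT counts.

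One lost DLT is enough to turn 2/6 into 1/6 or 1/3 into 0/3. This part rests only on the text and on a DLT-free replacement. The rise from 43% to 47-58% at a true rate of 1/3 rests on an assumed 10-30% share and on a committee that does not intervene; it shows direction, not an expected effect. Nothing in the documents shows that such a patient existed or that either escalation decision was wrong.

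**What to change.** 1. In Protocol 13.3.2, the synopsis and Phase 1 SAP 2.3.2, state that every treated patient with a committee-confirmed Cycle 1 DLT is DLT-evaluable and is not replaced, whatever the number of administrations or the reason for stopping. Only DLT-free patients who did not complete Cycle 1 are then non-evaluable. The missing-data sentence can remain for patients without a confirmed DLT.
2. Reconcile the denominator (evaluable in the synopsis, treated in 6.3) and the replacement wording (mandatory in 13.3.2, optional in 11.2), and correct the reference from 11.2 to 6.3.
3. Because escalation is complete, confirm in the study report that no patient with a Cycle 1 DLT was excluded from the evaluable population or replaced. If one was, show the DLT count both ways.

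The cost is one sentence in three places, two wording corrections and a check of the Phase I patient listings. No data collection or patient management changes.
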